**DEFINITIONS**

Adverse event:	“Any unfavourable and unintended sign, symptom, laboratory finding or disease which was absent at baseline, or if present at baseline, appears to worsen AND is temporally associated with the participants involvement in the research”
Apnoea:	No spontaneous breathing for either 20 seconds, or less than 20 seconds and associated with colour change; hypoxia (SPO 2 <88%) or bradycardia (heart rate <100 bpm)
Low birth weight:	Birth weight 1500 - 2499g
Very low birth weight	Birth weight 1000 - 1499g
Extremely low birth weight:	Birth weight less than 1000g
Neonatal period:	Period from birth to 28 days
Early neonatal period:	0 – 6 days after birth
Late neonatal period:	7 – 28 days after birth
Neonatal mortality rate:	Number of neonates dying before 28 days of age, per 1000 live births per year
Preterm birth:	Birth at <37+0 completed weeks gestation
Extreme preterm:	Birth at <28+0 weeks gestation
Very preterm:	Birth at 28+1 – 31+6 weeks gestation
Moderate-late preterm:	Birth at 32+0 – 36+6 weeks gestation
Serious Adverse event:	Any untoward medical occurrence which:  a) Results in death b) Is life threatening (Neonatal Near Death) c) Requires prolonged hospitalisation d) Results in persistent or significant disability / incapacity

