## Protocol summary

Title:	A randomised controlled trial of early continuous skin-to-skin contact versus standard care on survival of hospitalised unstable neonates <2000g in The Gambia
Alias :	eKMC
Population:	392 hospitalised mild-moderately unstable neonates weighing <2000g and aged 1 – 24h
Number of participants:	392 newborns (ratio 1:1)
Number of Sites:	1 recruitment site
Location of Sites (including satellite sites):	Neonatal unit at Edward Francis Small Teaching Hospital, Banjul, The Gambia
Trial Duration:	Recruitment over period of 24 months
- Clinical Phase:	Whole trial: 25 months
Duration for Participants:	Neonates will be followed up from enrolment within 24h after birth to 28 days Mothers/caregivers will be consented for paired biological swab samples at/shortly after admission
Description of intervention:	Kangaroo mother care is a package of care for preterm/low birth weight (LBW) neonates consisting of: prolonged skin to skin contact; promotion of early & exclusive breast milk feeding; early hospital discharge with close follow up. Intervention arm: Subjects will receive the continuous skin-to-skin contact aspect of KMC as soon as possible within 24h after admission Control arm: Subjects will be managed in incubators or radiant heaters, as per standard care, with skin-to-skin contact (KMC) started when clinically stable at >24h of admission
Objectives:	Objective 1. To assess the effect of early continuous skin-to-skin contact on survival of hospitalised, mild-moderately unstable neonates weighing <2000g  Objective 2. To assess the effect of early continuous skin-to-skin contact on other important clinical outcomes for hospitalised, mild-moderately unstable neonates weighing <2000g  Objective 3. To assess the safety of early continuous skin-to-skin contact in the hospital management of mild-moderately unstable neonates <2000g

Protocol #: 1

---

Objective 4. To explore early (thermal control, cardio-respiratory stability) and late (infection prevention control, gastro-intestinal stability) mechanistic pathways for the beneficial effects of early continuous skin-to-skin contact compared to standard care in hospitalised, mild-moderately unstable neonates weighing <2000g.

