## **5.8 Follow-up**

Participants will be followed up daily during the hospital admission (see clinical evaluations, section 6.1.2). If participants are discharged before day 7, they will be phoned on day 7 to ascertain outcome (alive, died, re-admitted) and asked to come to the clinic when 28 days old. If participants are discharged between day 7 and day 28, they will be asked to return to the routine KMC unit clinic on day 28 of life where they will have repeat swab samples (skin, rectal) taken, undergo anthropometry and document feeding practices and outcome (alive; dead). If 28 days falls on a weekend, they will be asked to come on the closest working day (E.g. if a Saturday, come on Friday, if day 28 is Sunday, to come on Monday) with a window period of 5 days (28 days +/- 5 days). If participants do not attend follow-up clinic a telephone call will be made the same day to ascertain outcome and feeding practices and to arrange follow-up as soon as possible. Routine follow-up out with the planned study follow-ups will be provided by the study site staff according to standard practice and clinical need of the baby.

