## **5.10 Final study visit**

The final study visit will be at the hospital KMC unit clinic at 28 days of age, as described in section 5.4.6.

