### **6.1.2 Evaluations from 24h to hospital discharge**

Starting at 48h of study participation, all subjects will be followed up daily until admission to the KMC unit and then weekly on day 7, 14, 21, 28 of life during the KMC unit stay. If a baby requires re-admission to the neonatal unit the reviews will restart every day until KMC unit admission or discharge from the neonatal unit. The following actions will be done using study specific equipment:

- a. Daily review with the following trial assessments documented:
  - Date and time of starting breast milk feeding and date that full breast milk feeding is established
  - Date and time of starting breastfeeding
  - Daily recording of IV fluid volumes, drip rates and medications given
  - Daily measurement of vital signs (heart rate, respiratory rate, oxygen saturation, temperature, blood glucose)
  - Compliance with the standardised management protocol and discussion of any deviations with study site medical team
- Documentation of details about skin-to-skin contact:
  - Date and time of skin-to-skin contact initiation
  - Duration of skin-to-skin contact/day
  - Person providing skin-to-skin contact

Protocol #: 1

- Whether skin-to-skin contact is temporarily discontinued and date/time of this event
- Documentation of patient flow through the ward Identification and documentation of any change in clinical condition warranting temporary cessation of intervention and date/time of temporary cessation
- Identification of any SAE

b. Weighed on day 5, then daily until discharge(to be done at an appropriate time in collaboration with study site staff and clustered with other procedures, E.g. changing of nappies)

c. OFC and length to be measured weekly using study equipment

d. Neonatal skin and rectal swab sample to be taken on days 7 and 28 if still an inpatient or attending outpatient clinic

Study site staff will be responsible for the ongoing medical and nursing management of the neonate according to the standardised management protocol with input from the study team if requested.

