### 8.3 Serious adverse events (SAEs)

The definition of SAE for this study is:

- Death
- Life threatening event
  - Apnoea needing bag-valve-mask ventilation but not resulting in death
  - Severe instability (as per protocol definition)
  - Any other life threatening situation as assessed by clinician
- At risk of permanent / temporary disability
  - Clinically suspected or microbiologically confirmed meningitis
  - Severe jaundice needing phototherapy/exchange transfusion

Protocol #: 1

---

- Suspected Hypoxic Ischaemic Encephalopathy (moderate-severe)
- Acquired hydrocephalus needing diuretics or surgical intervention
- Re-admission to hospital following discharge and within 28d of age
- Prolonged hospitalisation for 28 days or greater

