#### 8.5 Reporting procedures

To monitor for the incidence of adverse events (AE) during the period of hospitalisation, study personnel will review participants daily.

Any adverse events will be recorded in the standardised medical record and eCRF, including any treatments used by study site staff. Study site staff will be responsible for treating any AE with input from the research clinician and PI, as requested. The research clinician will review all AE and classify serious adverse events according to the protocol. All SAE will be reviewed by the PI or delegate within 24h of notification.

The PI or delegate will send an initial notification to the local safety monitor (LSM), sponsor and Clinical Trials Support Office at MRCG within 24h of first being aware. The initial detailed SAE report will be sent to LSM, sponsor and CTSO within 2 working days if the baby dies, or within 5 working days if the baby does not die. The DSMB will receive a 2 monthly summary safety report of all SAE's, as per DSMB charter. Any SAE thought to be related to the intervention will be reported to the ethics committees within 7 days if it results in death or 14 days if non-fatal. All SAE's resulting in death but not related to

Protocol #: 1

the intervention will be submitted to ethics committees as a monthly summary. All other (non-fatal) SAE's will be reported as an annual safety report to ethics committees and the sponsor.

Reporting procedures will be outlined in an Adverse Event SSP. All SAE reports or other safety reports will be kept as essential documents in the Trial Master File.

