### **6.5 Harms**

Adverse events and SAEs will be listed and defined with reference to standardised criteria where appropriate. The methods used for data collection and attribution of events will be described.

The number and proportion of participants with an SAE (life-threatening event; risk of disability; re-admission to hospital or prolonged hospital stay >28d) will be presented for both arms. Death will not be included as this is the primary outcome of the trial.

A detailed analysis of blood glucose levels over the first 24h of study participation will be performed as a proxy indicator of disturbance to the IV fluid administration. This will involve number and proportion of participants with hypoglycaemia or hyperglycaemia at defined time points as well as mean glucose level at baseline, 12h and 24h. The significance level will be calculated using chi squared or Fisher's exact tests for categorical variables. Continuous variables will be compared using Student's *t*-test or nonparametric tests, when appropriate. The appropriate effect size will be presented, using risk ratios for binary outcomes and difference between means for continuous data.

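### SAP 6.5 counts a prolonged stay as an SAE only above 28 days, but the protocol counts it from 28 days, so a 28-day stay drops out of the safety table

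*SAP*

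**What the plan says.** SAP 6.5 (Harms) will present, by arm, the number and proportion of participants with an SAE. Death is left out because it is the primary outcome. The remaining components are life-threatening events, risk of disability, and "re-admission to hospital or prolonged hospital stay >28d". SAP 4.4.2 sends the reader to section 6.5 for SAEs, so this list serves as the SAP's working definition.

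Protocol 8.3 gives the trial's SAE list and includes "Prolonged hospitalisation for 28 days or greater". The general definition at the front of the protocol says only "Requires prolonged hospitalisation", with no number of days, and so fits either rule. Protocol 8.5 has the research clinician classify SAEs according to the protocol, with a summary to the DSMB every two months and non-fatal events in an annual report.

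On follow-up, the protocol summary states "Neonates will be followed up from enrolment within 24h after birth to 28 days", and Protocol 5.10 adds "The final study visit will be at the hospital KMC unit clinic at 28 days of age". Babies in the KMC unit are reviewed "weekly on day 7, 14, 21, 28 of life during the KMC unit stay". Protocol 5.8 describes the day-28 clinic visit "with a window period of 5 days (28 days +/- 5 days"), and SAP 3.6 uses the same window.

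**The concern.** Two current documents define one SAE component with different limits, and the difference is not explained. SAEs were collected and sent to the DSMB, sponsor and ethics committees under the protocol's rule. If the final table is built under the SAP's rule, a reader comparing it with those reports may find fewer prolonged-stay SAEs and no explanation.

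The component is also sensitive to the intervention. Prolonged stay is one of four SAE components left once death is excluded. Duration of admission is a secondary outcome, and Protocol 1.1 expects KMC to shorten hospitalisation. A cut-off on a variable that may differ between arms should be fixed and unambiguous before the arms are compared, particularly as safety is Objective 3.

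The limit also falls close to the day-28 assessment, so the way days are counted can decide whether a baby is classified as an SAE.

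**Working it through.** There is no stated figure to reproduce: neither document says how many prolonged stays were expected. The check is a comparison of the two rules, followed by simple arithmetic on length of stay.

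**1. The two rules**
- Protocol 8.3: SAE if stay ≥ 28 days.
- SAP 6.5: SAE if stay > 28 days.
- Below 28 days neither rule is met, and above 28 days both are. They differ only when the stay is counted as exactly 28 days.

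**2. What exactly 28 days means depends on the counting convention, which neither document states for this item**
- In elapsed time (days and hours), the rules differ only at 28 d 0 h, so almost no baby is affected.
- In completed days, a count of 28 covers every stay from 28 d 0 h to just under 29 d. The SAP rule then requires at least 29 completed days, so a full day's range of discharges is reclassified.

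**3. Position relative to the day-28 assessment**
Inputs: age at screening 1 to 24 h (Protocol 4.2.1). Screening follows admission, so age at admission is 0 to 1 day. Elapsed stay = age at assessment − age at admission.

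| Age at assessment (days) | Elapsed stay (days) | > 28 met? | ≥ 28 met? |
|---|---|---|---|
| 23 | 22 to 23 | no | no |
| 28 | 27 to 28 | no | only at the limit |
| 29 | 28 to 29 | possible | yes |
| 30 | 29 to 30 | yes | yes |
| 33 | 32 to 33 | yes | yes |

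At 28 days of age the SAP rule cannot be met in elapsed time, but the protocol's rule is hardly met either. A snapshot at that age fails under both rules because admission comes after birth. The choice between > and ≥ is not the cause.

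**4. Whole-day counts on day 28 of life**
Stay = 28 − (number given to the day of birth, 0 or 1) − (days from birth to admission, 0 or 1) + (1 if both end days are counted, otherwise 0). The eight combinations give 28, 29, 27, 28, 27, 28, 26 and 27. The SAP rule is met in 1 of 8 and the protocol's rule in 4 of 8. The counting convention therefore matters as much as the inequality sign.

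**5. Is length of stay known past day 28?**
- The protocol's definitions run duration of admission from admission until discharge, with no cut at 28 days.
- SAP 3.6 assesses it on the day of discharge.
- Protocol 6.1.4 puts the date and time of discharge on the eCRF, and Protocol 11.1.3 also takes the discharge date from ward books.
- Protocol 8.5 ties safety review to the in-patient period: "To monitor for the incidence of adverse events (AE) during the period of hospitalisation, study personnel will review participants daily".

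The data needed to apply either rule to the whole stay are therefore planned. Classified from those dates, a baby who stays beyond 28 days is an SAE under both documents, and only stays counted as exactly 28 days are lost.

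**The case against.** The strongest reply is that the SAP's parenthesis is shorthand for the protocol's categories. SAEs were classified as the trial ran under the protocol, and SAP 6.5 says they will be listed and defined in the report. An analyst might simply tabulate the SAE flags in the database, and then nothing is lost. That is possible, but the SAP does not say so. It writes a specific and different limit, and SAP 4.4.2 treats that section as the reference for SAEs. The reply shows that the table could still reconcile; it does not remove the contradiction.

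It is also fair that the effect on the reported line is diluted. SAP 6.5 counts participants with any SAE, so a baby with a 28-day stay who also had apnoea needing bag-valve-mask ventilation, severe instability or a re-admission is counted anyway. No hypothesis test is specified for the SAE proportion. Both points stand.

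A reader might infer something stronger: that babies are followed only to 28 days of age, so the SAP rule misses every baby still in hospital at the final visit. The documents do not support this. Duration of admission is a secondary outcome measured to discharge, and discharge dates are recorded. The day-28 assessment has a window of 5 days either side, although Protocol 5.8 writes it for discharged babies. The protocol's own rule would also miss most babies judged at exactly 28 days of age. What remains of this reading is a gap: neither document says outright that a baby still in hospital at the day-28 review is tracked to discharge for SAE purposes. Nor do the documents support a count of affected babies, because any assumed proportion still in hospital would have no source.

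**Conclusion.** The inconsistency is real, current and unexplained. If the SAP is followed literally, stays counted as exactly 28 days are SAEs under Protocol 8.3 and absent from the SAP's by-arm table, so the table need not match the SAEs already reported.

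The size is small. It is limited to stays of exactly 28 days, and the participant-level count falls only for those babies with no other SAE. The number cannot be derived from the documents: the lower limit is zero, and the upper limit depends on the length-of-stay distribution and the counting convention. This conclusion assumes that stays are classified from recorded admission and discharge dates, which the documents plan to collect. The primary analysis, the sample size of 392 and the significance level are unaffected. It is a minor correction, worth making because it removes an ambiguity in a safety table.

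**What to change.** In SAP 6.5, replace the limit of more than 28 days with the protocol's limit of 28 days or more, so that both documents use one definition. Add that:

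- length of stay is computed from the recorded admission and discharge dates under a single stated convention (elapsed time or completed days, and whether the end days count);
- babies still in hospital at the day-28 review are followed to discharge for this item.

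Do not add a separate rule that counts every in-patient at 28 days of age. Elapsed stay at that age is only 27 to 28 days, so such a rule would be a third definition matching neither document, and it would undo the reconciliation the change is meant to secure.

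The cost is about one line of SAP wording. Discharge dates are already needed for the duration-of-admission outcome, so little or no new data collection is involved. The only downside is at most a few more SAEs in the table. SAP 3.5 places posting of the SAP before database closure and before any analysis, which is when the change should be made.

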#### *Kangaroo mother care is an evidence-based intervention for preterm/LBW hospitalised babies*

Kangaroo mother care (KMC) is recommended as standard care for all *stable*, hospitalised babies <2000g. It was developed in Colombia four decades ago and since adopted in both HIC and LMIC as an adjunct to incubator care. KMC is a complex intervention with the key component prolonged, continuous skin-to-skin contact between the nearly naked baby and mother's chest. The full definition, as described by Charpak et al, also includes promotion of early and exclusive breast-milk feeding, early discharge and close follow-up. Although other caregivers can provide skin-to-skin contact, a key aspect of KMC is the stimulation of maternal breast milk production and subsequent effects on feeding and growth.

Skin-to-skin contact and KMC are often used as synonyms in the literature, but for the purposes of this trial, early continuous skin-to-skin contact is considered the intervention under study.

Clinical benefits of KMC include reduced risk of: nosocomial infection; hypothermia, hypoglycaemia, severe infection and illness with moderate evidence of increased weight, length and head circumference gain and improved exclusive breast feeding at discharge, term and latest follow-up in *stable* neonates weighing less than 2000g. KMC also reduces duration of hospitalisation and hospital re-admission which benefits both neonate, mother and health care system. According to several systematic reviews, continuous KMC (>18h/day) reduces mortality by 36 - 51% compared to conventional incubator care. The most recent Cochrane review (2016) reported a 40% reduced risk of mortality at discharge or 40-41 weeks postmenstrual age (RR 0.60, CI 0.39-0.92; 8 trials, 1736 infants) and latest follow-up (RR 0.67, CI 0.48-0.85). However, this mortality effect is for "stable" neonates <2000g and there is an evidence gap for the mortality-effect of KMC in unstable babies within 24h after birth, when preterm/LBW babies undergo a physiological transition from in-utero to ex-utero life and are at greatest risk of mortality or near death events such as apnoea, hypoxia and bradycardia.

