At the end of the 10 minute period, if the baby meets all of the stable criteria they will be excluded and receive standard care. If criteria for mild instability are present, the subject will be recruited. If moderate or severe instability is present (definitions, page 10), continuous pulse oximetry will continue for further 2h 50 minutes (3 hours total) with a manual assessment of respiratory rate and breathing pattern at 3 hours. If the neonate meets any criteria of severe instability at any stage of the screening process, they will receive immediate medical management but will be excluded from the study only

Protocol #: 1

---

if they continue to meet severe criteria at the 3h assessment. All babies will receive standard medical management (E.g. oxygen, IV fluids, IV antibiotics) as indicated by the study site staff and standardised management protocol. All screening procedures will be documented on the screening log, which will record all new admissions weighing <2000g who undergo screening procedures and the outcome of the assessment. An eligibility checklist and flow chart will be used to assist the screening process. A screening number will be allocated.

It is estimated to take between 30 minutes and 3h 20 minutes to complete the screening process (Appendix 1. Overview of screening and enrolment procedures).

If the baby meets eligibility criteria but the caregiver is not present within 3h of the screening procedures, the 10 minute observation of cardio-respiratory stability will be repeated and documented once the caregiver is available and prior to informed consent. This is to ensure that the baby has not deteriorated in the intervening period.

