**5.7.2 Intervention arm**

Babies allocated to receive early continuous skin-to-skin contact will be naked except for hat and nappy and will be secured next to the exposed chest of the mother or caregiver using a KMC wrapper. The pulse oximeter will be attached to the subjects hand prior to placing baby in skin-to-skin position. These procedures will take place in the admission area, prior to moving the baby to the study area. On arrival at the study area, the mother/caregiver will be seated on the bed. The oxygen will be provided from an oxygen concentrator and attached to the nasal cannula. If the baby is on IV fluids, they will be connected to the IV cannula and the fluid bag securely hung, with drip rate calculated as per standard practice. Mothers/caregivers will be asked to continue skin-to-skin contact for as long as possible, aiming for minimum 18h/day but recognising that short breaks at regular periods will be necessary. If the mother/caregiver needs to take a short break, the baby will be placed in an incubator or under a radiant heater. Every effort will be made to encourage skin-to-skin contact for minimum 18h/day, unless otherwise clinically indicated and the mother/caregiver will be able to take short breaks as needed. The person providing skin-to-skin contact may change with substitute providers but a primary skin-to-skin, or KMC, provider

## Protocol #: 1

---

will be encouraged to avoid frequent disruption to the baby. The duration of skin-to-skin contact will be monitored. Once the subject is fully stable (definitions, page 10) and a bed is available, they will be transferred to the adjacent KMC Unit.

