**5.5 Baseline patient characteristics**

Baseline socio-demographic and clinical characteristics of the neonate, mother and perinatal period will be summarised for each arm by number and proportion (categorical variables) and either means with standard deviations or medians and interquartile ranges, as appropriate (continuous variables). This will include comparison of treatments received prior to enrolment. Statistical tests of differences in baseline characteristics will not be performed.

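### SAP 6.5 compares first-24h glucose across all babies with no baseline adjustment, so as a proxy for disturbed IV fluids it is diluted and less precise than the data allow

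*SAP*

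**What the plan says.** The glucose analysis in SAP 6.5 has one stated purpose: it "will be performed as a proxy indicator of disturbance to the IV fluid administration". Its content is also set out there: "This will involve number and proportion of participants with hypoglycaemia or hyperglycaemia at defined time points as well as mean glucose level at baseline, 12h"; the last time point listed is 24h. Categorical glucose outcomes are tested by chi-squared or Fisher's exact test, and for the rest "Continuous variables will be compared using Student's *t*-test or nonparametric tests, when appropriate". Section 6.5 names no covariates and makes no restriction to, or stratification by, receipt of IV fluids. It asks for effect sizes but gives no margin and no rule for reading a null result.

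IV fluids are conditional in both arms. At screening, "All babies will receive standard medical management (E.g. oxygen, IV fluids, IV antibiotics) as indicated by the study site staff" (Protocol 5.3.2). In the intervention arm, "If the baby is on IV fluids, they will be connected to the IV cannula" (Protocol 5.7.2). No document gives the proportion of babies on fluids.

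Baseline glucose is part of the clinical data collected after consent and before randomisation (Protocol 5.5 and 5.5.2). The covariates in SAP 6.2 are weight category, gestational age and twin status; baseline glucose is not among them.

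**The concern.** Skin-to-skin contact is given alongside IV fluids, and no other analysis in the SAP names disturbance of those fluids. If the signal can arise only in babies on fluids, including everyone else weakens it. A known, pre-allocation predictor of later glucose is also left out of the comparison, which gives up precision at no benefit.

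What is at stake is the sensitivity of one secondary safety analysis. With a diluted and noisier comparison, a real disturbance is more likely to go unseen.

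**Working it through.** **Inputs from the documents.** 392 babies allocated 1:1, so 196 per arm (Protocol 10.1, SAP 3.3). Significance level 0.05 (SAP 4.1), taken here as two-sided.

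**Inputs assumed, because the documents give none.** The share f of babies on IV fluids, the control rate of hypoglycaemia, the size of the harm, and the correlation ρ between baseline and later glucose. All figures treat babies as independent and assume a value for every baby.

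**1. The plan's own figure.** The glucose analysis has no sample size, power or margin of its own, so only the arm size is borrowed. With mortality of 0.48 against 0.48 × 0.70 = 0.336 and 80% power, the usual formula gives 182 per arm (364 in total). With the continuity correction it gives 196 per arm, or 392, matching the plan.

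**2. Dilution.** Let disturbance cause a difference δ in babies on fluids and none in the others. The difference in the full sample is f·δ, with a standard error proportional to 1/√n. In babies on fluids it is δ, with a standard error proportional to 1/√(f·n). With equal outcome variance, the ratio of test statistics (restricted to full) is √f / f = 1/√f.

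| f (assumed) | Full-sample difference | Gain from restricting |
|---|---|---|
| 0.5 | 0.5δ | 1.41 |
| 0.7 | 0.7δ | 1.20 |
| 0.9 | 0.9δ | 1.05 |

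**3. What that does to power.** Assume a control hypoglycaemia rate of 20% and a harm of 10 percentage points in babies on fluids.

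| f | Difference, all babies | Power, 196 per arm | Restricted n per arm | Power, restricted |
|---|---|---|---|---|
| 1.0 | 10 points | 62.9% | 196 | 62.9% |
| 0.8 | 8 points | 45.8% | 157 | 53.5% |
| 0.6 | 6 points | 29.1% | 118 | 42.6% |
| 0.4 | 4 points | 15.7% | 78 | 30.1% |

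At f = 0.6, power moves from 42% to 58% if the control rate is 10%, and from 24% to 36% if it is 30%.

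**4. Baseline adjustment.** Using baseline as a covariate multiplies the variance of the mean difference by 1 − ρ²: 0.96 at ρ = 0.2 and 0.75 at ρ = 0.5, a saving of 4% to 25%. The difference detectable with 80% power is (1.960 + 0.842) × √(2/196) × √(1 − ρ²). That is 0.283 SD unadjusted, 0.277 SD at ρ = 0.2 and 0.245 SD at ρ = 0.5.

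**5. What a null result could exclude.** With no true difference, the half-width of the 95% interval for hypoglycaemia in all babies is 1.96 × √(2p(1 − p)/196). For p = 10%, 20% and 30% this is 5.9, 7.9 and 9.1 points. On the scale of babies on fluids it must be divided by f: at p = 20% and f = 0.6, 7.9/0.6 = 13.2 points.

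**The case against.** The best reply is that this is a small matter. The SAP calls glucose a proxy and asks for effect sizes, and SAP 4.1 already commits to 95% intervals. Baseline glucose precedes allocation, so the unadjusted comparison is unbiased. The dilution is of unknown size, and at f = 0.9 the gain of 1.05 is negligible. The pilot tries out the intervention alongside IV fluids (Protocol 5.1), treatment discrepancies between arms are to be found and acted on (Protocol 3.5), and SAP 5.6 compares receipt of key management. All of this stands, although none of those provisions measures disturbance of fluids.

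A reader might also infer four stronger things that the documents do not support.

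- *That the plan would present equal glucose as proof of IV safety.* The SAP nowhere says so.
- *That a benefit of KMC would cancel the signal.* The protocol states: "Clinical benefits of KMC include reduced risk of: nosocomial infection; hypothermia, hypoglycaemia, severe infection and illness". The same sentence limits this evidence to stable neonates, whom the trial excludes (Protocol 4.2.2). Cancellation is arithmetically possible: with a 20% control rate, a KMC risk ratio of 0.8, 40% on fluids and a 10-point harm, the intervention rate is 0.8 × 20 + 0.4 × 10 = 20%, a net difference of zero. But every input is assumed, and nothing cited would offset hyperglycaemia, which is also analysed. It is a possibility, not a demonstrated defect, and restriction to babies on fluids would not remove it.
- *That SAP 6.5 contradicts SAP 5.5.* Section 5.5 says: "Statistical tests of differences in baseline characteristics will not be performed". Section 6.5 can be read as describing the baseline mean without testing it, so a contradiction is not established.
- *That fluid records already give a direct measure.* The protocol provides for "Daily recording of IV fluid volumes, drip rates and medications given" in reviews that start at 48h (Protocol 6.1.2). The first-24h evaluations in Protocol 6.1.1 list no fluid volumes or drip rates.

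**Conclusion.** The point holds as a modest, inexpensive improvement to a secondary harms analysis. Two features weaken the proxy: babies without IV fluids are pooled with those who have them, and an available pre-randomisation glucose is not used. The first costs a factor of 1.05 to 1.41 in the test statistic for an assumed share on fluids of 0.9 down to 0.5. The second costs 4% to 25% of variance for an assumed correlation of 0.2 to 0.5. That some babies have no IV fluids is inferred from the conditional wording, and the share could be high enough to make dilution trivial. Neither feature biases the comparison of arms as randomised. A non-significant glucose difference would still be weak evidence about IV fluids, and the SAP does not say how to read one.

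**What to change.** Amend SAP 6.5 as follows.

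1. Compare mean glucose at 12h and at 24h between arms in a linear model with baseline glucose as a covariate. Report the baseline mean by arm descriptively only.
2. Add an analysis restricted to, or stratified by, babies on IV fluids at randomisation. Status must be fixed before allocation so that the groups remain comparable.
3. Report confidence intervals for these comparisons, and state that a non-significant difference will not be taken as evidence of undisturbed IV fluids.
4. Compare IV volumes and drip rates by arm only if they turn out to have been captured in the first 24h.

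**Cost.** Item 1 uses data already planned. Item 3 is a sentence. Item 2 leaves fewer babies (118 per arm at an assumed share of 0.6), and a baby whose fluids start after randomisation would be classed as not on fluids. Treatments before enrolment are to be summarised under SAP 5.5, so IV status at randomisation should be recoverable, but the dataset must be checked to confirm this.
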